2.3.2 KNOWN POTENTIAL BENEFITS

The potential benefits of CD24Fc in patients with HIV infection included in the current study population are:

- Use of an agent as lipid-lowering therapy in the growing number of chronically infected HIV patients who have risk factors for cardiovascular disease and have underutilization of statins, resulting in sub-optimal cardiovascular disease risk modification
- Addressing the unmet medical need for decreasing immune activation and inflammation in patients infected with HIV, in order to reduce the risk of additional comorbidities and possibly lead to immune reconstitution

2.3.3 ASSESSMENT OF POTENTIAL RISKS AND BENEFITS

There is no intravenous treatment available to patients with HIV which is able to lower LDL and reduce inflammation/immune activation. Statins remain the standard of care for dyslipidemia, but are underutilized and may be ineffective in some cases. Other approaches, including ezetimibe, fibrates, and PCSK9 inhibitors, are approved therapies to lower LDL. However, CD24Fc has been found to lower LDL through different molecular mechanisms than statins and other approved drugs. CD24Fc may modulate the antigen presenting cells and promote immune reconstitution in HIV patients undergoing ART treatment. If favorable changes in immune activation, inflammatory markers, and LDL can be achieved in patients who receive a 4-week regimen of CD24Fc, the anticipated value of lowering cardiovascular risk with a safe and tolerable regimen offers a favorable risk-benefit determination.

3 OBJECTIVES AND ENDPOINTS

3.1.1 PRIMARY OBJECTIVES

- 1. To determine the safety and tolerability of CD24Fc during the 4-week dosing period and a 24-week follow-up period in a cohort of HIV patients.
- 2. To evaluate the change in LDL during a 4-week dosing period of CD24Fc and a 24-week follow-up period.

3.1.2 SECONDARY OBJECTIVES

To evaluate the effect of CD24Fc on the following variables between the placebo and intervention arms in comparison with baseline values:

- 1. Levels of total cholesterol, HDL, and triglycerides
- 2. Markers of immune activation (CD4 and CD8 T cells, IFN, TNF, sCD14)
- 3. Size of HIV reservoirs
- 4. Myocardial damage (measured by Troponin I and T)
- 5. Hepatic steatosis, as determined by transient elastography
- 6. Leptin
- 7. Hemoglobin A1c

- 8. Presence of anti-drug antibody (ADA) and temporal correlation to any adverse events, and its effect on PK (For first 6 subjects).
- 9. The pharmacokinetics (PK) and pharmacodynamics (PD) of CD24Fc in the first 6 randomized subjects.
- 10. Changes in IL-6, apoB, Lp(a), urine albumin to creatinine ratio before and after treatment.

3.1.3 EXPLORATORY OBJECTIVES

- 1. To assess the effect of CD24Fc on aortic vascular inflammation as measured by standardized uptake value of arterial FDG by PET/CT. We will select 12 subjects with an LDL>125 to have the imaging study.
- 2. To assess the effect of CD24Fc on the inflammatory markers hs-CRP and GlycA.
- 3. To assess the effect of CD24Fc on the CEC and NMR lipoproteins.
- 4. To assess the effect of CD24Fc on endothelin-1.

3.1.4 PRIMARY ENDPOINTS

- 1. Incidence and severity of any adverse events (AEs) during the administration of drug and 24 weeks after completion. Safety will be evaluated by assessment of clinical laboratory tests, physical examination at various time points during the study, and by the documentation for AEs.
- 2. The percentage reduction in LDL level from the baseline (predosing) to 2 weeks after the last treatment.

3.1.5 SECONDARY ENPOINTS

- 1. Percent change in levels of total cholesterol, HDL, and triglycerides from baseline to Week 6 and 28 between placebo and intervention arms.
- 2. Percent change in markers of immune activation (CD4 and CD8 T cells, IFN, TNF, sCD14) from baseline to Week 6 and 28 between placebo and intervention arms.
- 3. Change in proviral DNA from baseline to Week 6 and Week 28 between placebo and intervention arms.
- 4. Percent change from baseline to week 28 in Troponin I and T between placebo and intervention arms.
- 5. Change in percent of hepatic steatosis (by CAP measurement) and fibrosis (by KPA) as determined by transient elastography from baseline to week 28 between placebo and intervention arms.
- 6. Percent change in leptin from baseline to Week 6 and Week 28 between placebo and intervention arms.
- 7. Percent change in hemoglobin A1c from baseline to Week 6 and week 28 between placebo and intervention arms.
- 8. PK and PD assessments (For 6 subjects)
- 9. Presence of ADA and its effect on PK in all subjects

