1.3 SCHEDULE OF ACTIVITIES (SOA)

	Screening ⁺ Day -55 to - 14	Day -55 to -1	Day -55 to -1#	Day 0	Wk 2*	Wk 4*	Wk 6^	Wk 16^	Wk 28^
Informed Consent	Х								
Medical History & Physical Exam ¹	Х			Х			Х	Х	Х
Height, Weight, and BMI	Х								Х
Vital Signs	Х			Х	Х	Х	Х	Х	Х
Medication Reconciliation	Х			Х	Х	Х	Х	Х	Х
Adverse Event Review and Evaluation				Х	Х	х	Х	Х	х
CMP, CBC with diff, PT/INR, Urinalysis	Х			Х	Х	Х	Х	Х	Х
CD4 count and HIV VL	Х			Х	Х	Х	Х	Х	Х
Hepatitis B panel (surface antigen, core antibody, surface antibody)	Х								
Hepatitis C Ab with reflex RNA	Х								
Hemoglobin A1c	Х						Х		Х
Lipid panel (Fasting)	Х		Х	Х	Х	Х	Х	Х	Х
Troponin I and T	Х						Х		Х
Leptin (Fasting)	Х		Х				Х		Х
ECG (once at Screening and Wk 6; pre-dose and 2 hrs post-dose during dosing visits)	х			Х	Х	Х	Х		
Serum hCG (women of child-bearing potential)	Х								Х
POC Urine hCG (women of child-bearing potential)				Х	Х	Х	Х	Х	
PK of ART and CD24Fc before (and 2 hrs post-dose for Day 0 to Week 4)- first 6 subjects				Х	Х	Х	х	Х	х
Anti-drug antibody%				Х			Х		Х
Immunology labs (for CD4:CD8, sCD14, proviral DNA), inflammatory cytokines	Х			х	Х	х	х	х	х
GlycA, CEC, NMR lipoproteins ²				Х			Х		Х
hsCRP, IL-6, apoB, Lp(a), UACR	Х			Х	Х	х	х	х	Х
Endothelin-1	Х								Х
CD24Fc Infusion		Ī		Х	Х	Х			
Transient elastography with CAP	Х		х						Х
FDG PET/CT (NIH) ³		Х							Х

* Screening tests within the last 8 weeks prior to screening visit that have been done as part of routine medical care or at an outside

facility can be used. Screening window of 8 weeks with more than 2 weeks between screening and Day 0.

*Study Visits for Weeks 2-4 include a window of +/-4 days

^Study Visit for Weeks 6, 16 and 28 include a window of +/- 1 week except for FDG PET/CT, which will include a window of +/-30 days

¹ Targeted history and exam will be performed as needed for symptoms or lab abnormalities

 $^{\rm 2}$ Only for subjects completing the optional FDG-PET/CT testing

³ See protocol section 8.1.1.2 for criteria leading to FDG PET/CT testing

If subject is not fasting at screening, may return for fasting labs and Transient Elastography prior to Day 0

% also done for suspected immune-related adverse events.

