2.2.1 PHARMACOLOGY AND TOXICOLOGY OF CD24FC

PK information from human studies is further described in section 2.2.3. In human studies, The C_{max} and AUCs of plasma CD24Fc increased proportionally to the doses administered, consistent with data in mouse and monkey. The plasma CD24Fc reached T_{max} between 1.01 and 1.34 hours. The $t_{1/2}$ of plasma CD24Fc ranged between 280.83 and 327.10 hours. More information is available in section 5 of the IB.

For information about nonclinical pharmacokinetics, please refer to sections 1.3 and 4.2 of the IB.

For more information about nonclinical pharmacology, please refer to section 4.1 of the IB.

For more information about toxicology in animals, please refer to section 4.3 of the IB.

For more information about safety pharmacology, please refer to section 4.4 of the IB.

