In total, there was a reduced rate of cytomegalovirus (CMV) reactivation at Day 100 in the CD24Fc treatment group over the placebo group (22.2% and 50.0%, respectively) among high risk populations (pre-transplantation CMV status as D+/R+, D-/R+, or unknown D/R+). The CMV reactivation in the 2 patients in the CD24Fc group occurred after systemic steroid treatment. The 1 patient in the placebo group with CMV reactivation did not receive steroid treatment prior to CMV reactivation.

 PK:

Following a single IV administration of CD24Fc (240 and 480 mg CD24Fc single dose cohorts), the geometric mean plasma exposure ($C_{max,-1d}$, AUC_{0-42d} , $AUC_{0-last,-1d}$, and AUC_{0-inf}) increased with increasing CD24Fc doses. The mean $t_{\frac{1}{2}}$ and λ_z were similar between the 240 and 480 mg doses of CD24Fc. The mean values of $t_{\frac{1}{2}}$ were 414.739 and 406.648 h and the mean values of λ_z were 0.0018 and 0.0017 h⁻¹ for the 240 and 480 mg CD24Fc single dose cohorts, respectively. Additionally, there was an increase in the mean V_z and CL between the 240 and 480 mg doses of CD24Fc.

Following multiple IV administrations of CD24Fc (960 mg CD24Fc multiple dose cohort), the exposure of CD24Fc was sustained over time. Additionally, the mean plasma CD24Fc concentration on Day 100 was higher for the 480, 240, and 240 mg (ie, 960 mg) CD24Fc multiple dose cohort (850.84 ng/mL) compared to the single dose cohorts (216.38 ng/mL and 330.96 ng/mL for the 240 and 480 mg CD24Fc single dose cohorts, respectively). Furthermore, the geometric mean AUC_{0-last,overall} value was higher for the 480, 240, and 240 mg (ie, 960 mg) CD24Fc multiple dose cohort (37,363,953.5 ng·h/mL) compared to the single dose cohorts (AUC_{0-last,-1d} of 10,156,549.9 ng·h/mL and 15,522,686.2 ng·h/mL for the 240 and 480 mg CD24Fc single dose cohorts, respectively).

The median $t_{max,-1d}$ (2.10 h for both the 240 and 480 mg CD24Fc single dose cohorts and 2.13 h for the 960 mg CD24Fc multiple dose cohort) was similar across all of the CD24Fc doses. For the 960 mg CD24Fc multiple dose cohort, the median $t_{max,-1d}$ and $t_{max,-2d}$ were similar (2.13 and 2.52 h, respectively).

Safety:

No patients experienced a DLT during the study. The MTD was not reached. The highest dose in this study, 960 mg CD24Fc multiple dose (ie, 480 mg, 240 mg, and 240 mg on Days -1, 14, and 28), is considered safe and recommended for future studies.

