8.1.1.7 WEEK 6 VISIT

At this visit, there will be vital signs, a medication reconciliation and documentation and review of adverse events. The first 6 subjects who had PK samples done at Day 0, Week 2, and Week 4 will also have PK blood samples obtained. The following laboratory tests will be done prior to drug dosing: CMP,

CBC, urinalysis, HIV VL, CD4, PT/INR, lipid panel, urine hCG (for females of child-bearing potential), HbA1c, immunology labs, IL-6, apoB, Lp(a), urine albumin:creatinine ratio, Hs-CRP. Subjects participating in the FDG-PET/CT will also have GlycA, CEC, and NMR lipoprotein collected. He/she must be fasting prior to blood draw.

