8.1.1.8 WEEK 16 VISIT

At this visit, vital signs, H&P and medication reconciliation will be done, as well as documentation and review of adverse events. The first 6 subjects who had PK samples done at Day 0, Week 2, Week 4, Week 6 will also have PK blood samples obtained. The following laboratory tests will be done: CMP, CBC, urinalysis, HIV VL, CD4, PT/INR, hemoglobin A1c, lipid panel, leptin, troponin I, urine hCG (for females of child-bearing potential), , IL-6, apoB, Lp(a), urine albumin:creatinine ratio, anti-drug antibody, and research immunology and inflammation labs.. He/she must be fasting prior to blood draw.

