Although CD24Fc is not expected to have anti-viral activity, preliminary studies in humanized mice and non-human primate models ³⁰, showed that CD24Fc significantly reduced viral burden in vivo, including proviral burden in the PBL of SIV-infected Macaques rhesus, perhaps by preventing T cell over-activation and its associated exhaustion immunity³⁰. This hypothesis will be tested in ART-treated HIV infected subjects by longitudinal analysis of proviral titers. Established methods for quantification of proviral DNA (droplet digital PCR) will be used as described^{31,32}. Droplet digital PCR will be conducted to quantitate the frequency of cells carrying HIV proviral DNA and cell-associated HIV RNA with single copy sensitivity. The level of replication-competent/infectious HIV in the CD4⁺ T cell compartment will be determined by quantitative coculture assays.

• Inflammatory cytokines

Peripheral blood mononuclear cells will be isolated using Ficoll-Hypaque density gradient technique and used for immunophenotyping. Cells will be washed and stained using appropriate panels of monoclonal antibodies that distinguish cell type (B, T NK, monocyte etc.), cellular

activation states (CD14, CD38, HLA DR, CD25, etc.) and their ability to secrete inflammatory cytokines (IFN, TNF) using intracellular cytokine staining using a 12 color flowcytometry analysis with FlowJo software, at the University of Maryland.

- CD4 and CD8 T cell counts and ratio
 T cell immunophenotyping will be performed as a clinical laboratory test using flow cytometry at the University of Maryland.
- GlycA, plasma. This is a heterogeneous nuclear magnetic resonance signal originating from mobile glycan residues on plasma glycoproteins, used as a novel composite biomarker of systemic inflammation. This assay will be done at the NIH for those subjects completing the optional FDG-PET/CT.
- CEC- cholesterol efflux capacity, plasma. This is an assay assessing HDL function using the macrophage J774 efflux system. This assay will be done at the NIH for those subjects completing the optional FDG-PET/CT.
- NMR lipoproteins, plasma. This is an assay looking at lipoprotein particle size and number using NMR spectroscopy. This assay will be done at the NIH for those subjects completing the optional FDG-PET/CT.
- Endothelin-1, plasma. An ELISA test will be done for subjects at screening and week 28 to look for changes in endothelin-1, which may indicate changes in pulmonary arterial pressure.

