9.4.2 ANALYSIS OF THE PRIMARY EFFICACY AND SECONDARY ENDPOINTS

The primary efficacy and secondary analysis will be based on the mITT set. Most of primary and secondary variables such as T cell surface markers and plasma cytokine levels, and change and percent change from baseline to week 28 on markers of vascular inflammation and myocardial damages will be viewed as continuous variables and transformed as necessary. Each of efficacy variables will be analyzed using an Analysis of Covariance (ANCOVA) model with treatment as the fixed effect and other potential risk factors such as baseline value, clinical measures and demographic information as covariates. Differences between treatment groups and 95% confidence intervals will be estimated within the framework of ANCOVA. The statistical test for each of those variables will be a two-sided test at a significance level of 0.05 and no multiplicity adjustment will be done.

Specific details will be provided in the full statistical analysis plan (SAP) for the study.

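### Secondary endpoint 4 tests Troponin I and T only at Week 28, about 10 to 14 half-lives after the last dose, although the Schedule of Activities already draws troponin at Week 6

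*Combined protocol and SAP*

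**What the plan says.** Secondary objective 4 (Section 3.1.2) is the effect of CD24Fc on myocardial damage, measured by troponin. The matching endpoint in Section 3.1.5 is "Percent change from baseline to week 28 in Troponin I and T between placebo and intervention arms". The Synopsis, Section 9.1 and Appendix A state the same endpoint. Section 9.4.2 names "change and percent change from baseline to week 28 on markers of vascular inflammation and myocardial damages" among the ANCOVA variables. The copy of that sentence in Appendix A gives Week 36, which is later than the last visit.

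The places that govern when troponin is drawn do not agree:

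- The Schedule of Activities (Section 1.3) has a row "Troponin I and T" marked at Screening, Week 6 and Week 28.
- The Week 6 visit text (Section 8.1.1.7) omits troponin. Its list includes "HbA1c, immunology labs, IL-6, apoB, Lp(a), urine albumin:creatinine ratio, Hs-CRP".
- The Week 16 visit text (Section 8.1.1.8) includes "hemoglobin A1c, lipid panel, leptin, troponin I, urine hCG", but the Schedule marks no troponin at Week 16.

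For endothelin-1, an exploratory marker, Section 8.2 says: "An ELISA test will be done for subjects at screening and week 28 to look for changes in endothelin-1". Its endpoint wording names no week, so Week 28 as the only post-baseline value follows from the sampling.

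Half-lives are given twice. In healthy subjects they "ranged between 280.83 and 327.10 hours" (Section 2.2.1). In the Phase IIa transplant patients the means "were 414.739 and 406.648 h" for the 240 and 480 mg single doses (Section 2.2.3).

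**The concern.** The objective asks what the drug does to the heart muscle, and the only planned comparison is made 24 weeks after dosing ends. The plan treats its other blood markers differently. Lipids, immune activation markers, proviral DNA, leptin and HbA1c are each assessed at Week 6 and Week 28, and the primary LDL endpoint is at Week 6. Troponin is the only blood-based secondary endpoint with named weeks that is confined to Week 28. Section 8.1.1.9 explains late timing for elastography and for FDG-PET/CT, but gives no reason specific to troponin.

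What is at stake is the reading of a null result. If troponin moved in either direction during exposure and then returned to baseline, the endpoint as defined could not show it. The Week 6 sample that could show it has no between-arm contrast attached. A sample that serves no endpoint, and that the Week 6 visit text leaves out, is also easy to miss at the site.

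**Working it through.** **Inputs.** Doses at Day 0, Week 2 and Week 4 (Schedule of Activities). Half-lives of 280.83 and 327.10 h (Section 2.2.1), and 406.648 and 414.739 h (Section 2.2.3). Visit windows of ±4 days at Week 4 and ±1 week at Weeks 6 and 28 (Schedule footnotes).

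**The plan's own interval.** Week 28 − Week 4 = 24 weeks, which matches the stated follow-up period. In hours, 24 × 168 = 4,032. Week 6 − Week 4 = 2 weeks, and 2 × 168 = 336 h.

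**Formulas.** Half-lives elapsed n = hours since last dose ÷ half-life. Fraction remaining = 0.5^n. With one exponential rate, earlier doses decay in the same proportion, so the fraction of the level after the third dose does not depend on accumulation.

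| Half-life (h) | n at Week 6 | Remaining at Week 6 | n at Week 28 | Remaining at Week 28 |
|---|---|---|---|---|
| 280.83 | 1.20 | 43.6% | 14.36 | 0.005% |
| 327.10 | 1.03 | 49.1% | 12.33 | 0.019% |
| 406.648 | 0.83 | 56.4% | 9.92 | 0.104% |
| 414.739 | 0.81 | 57.0% | 9.72 | 0.118% |

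**Visit windows at their extremes.** The combined shift is 4 + 7 = 11 days. Week 28 then falls 157 to 179 days after the last dose:

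- 157 × 24 ÷ 414.739 = 9.1 half-lives
- 179 × 24 ÷ 280.83 = 15.3 half-lives

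Week 6 falls 3 to 25 days after the last dose:

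- 3 × 24 ÷ 414.739 = 0.17 half-lives
- 25 × 24 ÷ 280.83 = 2.14 half-lives

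The contrast between the two visits survives any combination of windows.

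**Which contrasts are planned.** Troponin: Week 28 only, in the endpoint lists and in Section 9.4.2. Week 6 troponin: no between-arm test in any section. Section 9.4.3 summarises laboratory values by arm at baseline, post baseline and as change, and states that safety data will have no inferential analysis.

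**The case against.** **There is an indirect reason for Week 28.** Section 8.2 introduces troponin alongside the vascular inflammation measurement, Section 9.4.2 groups the two, and Section 8.1.1.9 explains why the scan comes late. This stands as a reason to keep Week 28. It does not explain leaving out Week 6: the scan is for 12 participants, troponin is for all, and the Schedule already takes the earlier sample.

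**Drug level is not drug effect.** This also stands. The half-lives are single-dose values from healthy and transplant subjects, and a terminal half-life applied from the post-dose level ignores any distribution phase, so 44% to 57% may be high. A reader might infer that no effect can be seen at Week 28. The documents do not support that, because a lasting downstream effect is possible.

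**Week 6 troponin is not necessarily unreported.** A reader might infer that it would appear nowhere. It could appear in the Section 9.4.3 summaries, and analysis detail is deferred to a SAP to be finalised before unblinding. But a descriptive summary does not test a secondary objective, and the protocol's endpoint and analysis text name Week 28 only.

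**There is no established myocardial signal.** A reader might link this point to the drug-related serious event in Phase I. That event was non-sustained ventricular tachycardia, judged mild and occurring at a rate comparable with normal populations. The documents report no myocardial injury from it. Arrhythmia has its own safeguards: an exclusion criterion, ECGs around each infusion and an ECG at Week 6.

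**Endothelin-1 is a different case.** A reader might give it the same weight. It is exploratory, its endpoint names no week, and a Week 6 value would need new assays.

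**Conclusion.** The point holds for troponin. The endpoint and its analysis are confined to a visit 9.7 to 14.4 stated half-lives after the last dose (9.1 to 15.3 with visit windows at their extremes), while a scheduled sample at 0.8 to 1.2 half-lives has no between-arm contrast. A reversible on-exposure effect would therefore go untested.

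The conclusion rests on two assumptions: roughly exponential decline, and half-lives in people with HIV after three doses similar to those reported elsewhere. The gap between the visits is wide enough that moderate error in either would not change it. It also relies on the Schedule of Activities for the Week 6 draw, which the Week 6 visit text does not confirm.

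This is a gap in a secondary endpoint. It does not affect the primary endpoints or the sample size, and it does not show that the drug harms the heart or that Week 28 is uninformative.

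**What to change.** 1. Define secondary endpoint 4 as percent change in Troponin I and T from baseline to Week 6 and to Week 28, in Sections 1.1, 3.1.5 and 9.1 and in Appendix A.
2. Align Section 9.4.2 with this, and correct the Appendix A copy that refers to Week 36.
3. Reconcile the Schedule of Activities with the Week 6 text, which omits troponin, and the Week 16 text, which lists Troponin I, so that the Week 6 sample is certain to be taken.
4. State that Week 6 describes the period with drug present and Week 28 describes persistence after washout.
5. For endothelin-1, either state that the Week 28 result describes only the post-washout period or, optionally, add a Week 6 sample.

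**Cost.** For troponin: wording and reconciliation, with no new visit and no new row in the Schedule. There would be two more secondary comparisons (Troponin I and Troponin T), each at 0.05 without adjustment under Section 9.4.2. That adds 2 × 0.05 = 0.10 expected false positives if neither marker is affected. The endothelin-1 option needs about 64 extra assays and assumes that the existing Week 6 blood draw can supply the plasma.

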3.1.6 EXPLORATORY ENDPOINT

- Change in vascular inflammation as evidenced by aortic FDG uptake by FDG-PET/CT will be assessed before and after therapy. The arterial uptake of FDG is measured by the standardized uptake value (SUV) max divided by the venous SUV mean yielding a target to background ratio (TBR).
- 2. Changes in hs-CRP and GlycA before and after treatment.

- 3. Changes in CEC and NMR lipoproteins before and after treatment.
- 4. Changes in endothelin-1 before and after treatment.

